### **9.3.3 Analysis of Other Secondary Variables**

#### **9.3.3.1 Definition of Variables**

Time-to-first PEx through Week 24: the number of days from the first dose date of study drug to the date of the first pulmonary exacerbation during the PEx analysis period. A subject who does

not experience a PEx during the PEx analysis period will be censored at the PEx analysis period end date.

BMI z-score: the BMI score, adjusted for age and sex, will be referred to as BMI-for-age z-score (BMI z-score). The BMI z-score will be calculated by using Centers for Disease Control and Prevention (CDC) growth charts, with the age (in months) used for the calculation defined in [Appendix A](#).

[figure not shown]
### 9.3.3.2 Analysis Method

Time-to-first PEx through Week 24: Time-to-first PEx will be analyzed using the Cox regression model. The model will include a fixed effect for treatment, as well as continuous baseline ppFEV1, age at screening (<18 versus ≥18 years of age), and sex (male versus female) as covariates. Additionally, the Kaplan-Meier method will be used to produce a graphical presentation of the cumulative exacerbation-free rate for each treatment group and to estimate the cumulative exacerbation-free rate by treatment group.

[figure not shown]
Note: If the number of events is <5 in either treatment group, Cox regression will not be performed and the analysis of the time-to-first event will be restricted to the Kaplan-Meier method.

Absolute change in BMI z-score from baseline at Week 24 (for subjects ≤20 years of age at Baseline): Analysis of this variable will be based on an MMRM similar to the analysis of the primary efficacy variable, excluding the covariate of age at screening (<18 versus ≥18 years of age), for subjects ≤20 years of age at Baseline. Data obtained from Day 15, Week 4, Week 8, Week 12, Week 16, and Week 24 Visits will be included in the model.

Absolute change in body weight from baseline at Week 24: Analysis of this variable will be based on an MMRM similar to the analysis of the primary efficacy variable. Data obtained from Day 15, Week 4, Week 8, Week 12, Week 16, and Week 24 Visits will be included in the model.

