## **9.2 Method of Assigning Subjects to Treatment Groups**

Subjects will be randomized (1:1) to the TC VX-659/TEZ/IVA arm or to the triple placebo arm. Randomization will be stratified by ppFEV1 determined during the Screening Period (<70 versus ≥70), age at the Screening Visit (<18 versus ≥18 years of age), and sex (male versus female).

An interactive web response system (IWRS) will be used to assign subjects to treatment. The randomization code list will be produced by Vertex Biometrics or a qualified randomization vendor.

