#### **12.3.3.1 Final Analysis**

##### **12.3.3.1.1 Analysis of Primary Variables**

The primary efficacy variable is the absolute change in ppFEV1 from baseline at Week 4. The analysis of this variable will be performed using a mixed-effects model for repeated measures (MMRM) with change from baseline at Day 15, Week 4, Week 8, Week 12, Week 16, and

Week 24 as the dependent variable. The model will include treatment group, visit, and treatment-by-visit interaction as fixed effects, with continuous baseline ppFEV1, age at screening (<18 versus ≥18 years of age) and sex (male versus female) as covariates. The model will be estimated using restricted maximum likelihood. Denominator degrees of freedom for the *F*-test for fixed effects will be estimated using the Kenward-Roger approximation. An unstructured covariance structure will be used to model the within-subject errors. If the model estimation does not converge, a compound symmetry covariance structure will be used instead. Conditional on the observed data and covariates, missing data will be assumed to be missing at random; consequently, no imputation of missing data will be performed.

The primary result obtained from the model will be the estimated treatment difference at Week 4. The adjusted mean difference at Week 4 with 2-sided 95% confidence intervals and 2-sided *P* values will be provided. Furthermore, the adjusted mean and treatment difference at each post-baseline visit will also be provided, obtained from the model.

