### **Analysis of Other Secondary Variables**

Other secondary efficacy variables include:

- **Time-to-first PEx through Week 24:** Time-to-first PEx will be analyzed using the Cox regression model. The model will include a fixed effect for treatment, as well as continuous baseline ppFEV1, age at screening (<18 versus ≥18 years of age), and sex (male versus female) as covariates. A subject who does not experience a PEx during the PEx analysis period will be censored at the PEx analysis period end date. If the proportional hazards assumption is violated for any of the categorical covariates, a stratified Cox regression will be conducted. Additionally, the Kaplan-Meier method will be used to produce a graphical presentation of the cumulative exacerbation-free survival rate for each treatment group and to estimate the cumulative exacerbation-free survival rate by treatment group. Note: If the number of events is <5 in either treatment group, Cox regression will not be performed and the analysis of the time-to-first event will be restricted to the Kaplan-Meier method.
- **Absolute change in BMI z-score from baseline at Week 24 (for subjects ≤20 years of age at Baseline):** Analysis of this variable will be based on an MMRM model similar to the analysis of the primary efficacy variable, for subjects ≤20 years of age at Baseline. Data obtained from Day 15, Week 4, Week 8, Week 12, Week 16, and Week 24 Visits will be included in the model.
- **Absolute change in body weight from baseline at Week 24:** Analysis of this variable will be based on an MMRM model similar to the analysis of the primary efficacy variable. Data obtained from Day 15, Week 4, Week 8, Week 12, Week 16, and Week 24 Visits will be included in the model.

Additional details will be provided in the SAP.

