**Table 12-1 Analysis Visit Windows for Safety and Efficacy Assessments**

Assessment	Visit 	Target Study Day	Analysis Visit Window (in study days) 
Weight, Height and BMI (and the corresponding z-score)	Day 1 (Baseline)	1	≤1
	Day 15	15	(1, 22]
	Week 4	29	(22, 43]
	Week 8	57	(43, 71]
	Week 12	85	(71, 99]
	Week 16	113	(99, 141]
	Week 24	169	(141, 183]
	Safety Follow-up	Not applicable	>183

Notes:

 Visit name for analysis purpose is used to report data in tables and figures.

 The analysis visit windows will be applied using the following rules for both scheduled and unscheduled visits:

- If no numerical measurement is available within a visit window, the measurement will be considered missing for the visit.
- If there is more than 1 numerical measurement available within a visit window, use the following rules:
  - The measurement closest to the target day will be used; or
  - If there are multiple measurements with the same distance from the target day, the latest measurement will be used.

 For lab, ECG and vital sign measurement collected on the date of first dose of study drug, if it cannot be determined whether the measurement is before or after the first dose:

- Scheduled measurement will be treated as pre-dose observation.
- Unscheduled measurement will be treated as post-dose observation.

Derived Variables:

- Age (in years) at first dose date and nominal visit (for demographics, listing and the calculation of [percent] predicted spirometry variables):
 

Obtain the age at informed consent (in days) in “yy, mm” format (e.g., 24 years, 6 months) from the Vital Signs (VS) page at the Screening Visit, and add 0.5 month to convert to days.

Obtain the informed consent date.

Then age (in years) at first dose or nominal visit = [(first dose date or nominal visit date – informed consent date) in days + age at informed consent (in days)]/365.25.
- Age (in months) at nominal visit (for use in calculation of BMI and weight z-score):
 

Obtain the age at informed consent (in months) in “yy, mm” format (e.g., 24 years, 6 months) from Vital Signs (VS) page at the Screening Visit.

Obtain the informed consent date.

Then age (in months) at nominal visit = integer part of {(age at informed consent (in months) + 0.5 + diff(first dose date or post-baseline visit date, informed consent date) in months)} + 0.5.
- Missing first dose date or last dose date
 

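### SAP 9.3.3.2 drops the age stratum from the BMI z-score model: no bias and no inflated type I error, but possibly a small, avoidable loss of precision

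*SAP*

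**What the plan says.** - **Randomization.** Protocol 9.2 stratifies by screening ppFEV1 and by "age at the Screening Visit (<18 versus ≥18 years of age), and sex (male versus female". SAP 7.3 agrees.
- **Primary model.** Protocol 12.3.3.1.1 takes baseline ppFEV1 together with "age at screening (<18 versus ≥18 years of age) and sex (male versus female) as covariates". SAP 9.3.1.2 does the same.
- **BMI z-score in the protocol.** The section on other secondary variables specifies "an MMRM model similar to the analysis of the primary efficacy variable, for subjects ≤20 years of age at Baseline". It mentions no exclusion and closes with "Additional details will be provided in the SAP".
- **BMI z-score in the SAP.** Section 9.3.3.2 repeats the similar-to-primary description but adds "excluding the covariate of age at screening (<18 versus ≥18 years of age), for subjects ≤20 years of age at Baseline". The readable text gives no reason.
- **Other MMRM analyses.** BMI, sweat chloride and CFQ-R (SAP 9.3.2.2) and body weight (SAP 9.3.3.2) are modelled like the primary variable with no such exclusion.
- **The outcome.** SAP 9.3.3.1 defines it as "the BMI score, adjusted for age and sex, will be referred to as BMI-for-age z-score (BMI z-score"). It is computed from growth charts, and the SAP's Appendix A derives the age in months at each visit for that purpose.

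**The concern.** A model normally adjusts for the factors used in randomization, and nearly every other model in this plan adjusts for age. Here age is removed for one endpoint, in a subset where it still varies: entry is from 12 years, so the subset holds ages 12-17 and 18-20.

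Stratification balances the arms among subjects under 18 and among those 18 and over. It does not balance the 18-20-year-olds, who are only a slice of the upper stratum.

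If the 24-week change in z-score differs between the two age groups, leaving age out has two effects. The difference stays in the residual and widens the SE. Any chance excess of 18-20-year-olds in one arm also moves the estimate.

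Sex stays in the model although the score is sex-adjusted as well, so standardization alone does not explain why only age was dropped.

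**Working it through.** The plan states no sample size, SD, effect or power for BMI z-score, so there is no figure to reproduce. The numbers below show how large the loss could be under assumed inputs.

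**Inputs**
- From the documents: about 360 subjects randomized 1:1, age stratum <18 versus ≥18, subset aged 20 or younger at baseline.
- Assumed: 100 subjects under 18 and 40 aged 18-20 (so 360 − 100 = 260 in the ≥18 stratum); SD of change within an age group 0.35; treatment effect 0.17, which gives about 80% power.
- Varied: the between-stratum difference in mean change.

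**1. Imbalance in the 18-20 group.** If the 260 are split evenly between arms, the number of the 40 who fall in one arm is hypergeometric, with SD √(40 × 0.25 × 220/259) = 2.91. With 70 per arm, one extra subject changes the arm difference in the share aged 18-20 by about 2 × 50/70² = 0.0204. The SD of that difference is 2.91 × 0.0204 ≈ 0.06, or 6 percentage points. At a stratum difference of 0.2, a one-SD imbalance shifts the estimate by 0.06 × 0.2 = 0.012. That is 7% of the assumed effect, and about a fifth of an SE of 0.35 × √(4/140) = 0.059. The shift is as likely in either direction.

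**2. Width of the SE.** The SE without age divided by the SE with age is approximately √(1 + p(1−p)d²). Here p is the share aged 18-20, 40/140 = 0.286, so p(1−p) = 0.204. The term d is the stratum difference divided by 0.35.

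The last two columns come from 200,000 simulated trials per setting. The <18 stratum was split evenly and the 18-20 group drawn as in step 1. A two-sample t-test was compared with an ANCOVA on treatment and age, at two-sided 0.05.

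| Stratum difference | d | SE ratio (formula) | SE wider by (simulated) | Power without / with age |
|---|---|---|---|---|
| 0.05 | 0.14 | 1.002 | no loss | no loss |
| 0.1 | 0.29 | 1.008 | under 1% | 80.9% / 81.3% |
| 0.2 | 0.57 | 1.033 | 3.1% | 79.2% / 81.2% |
| 0.3 | 0.86 | 1.072 | 7.1% | 76.5% / 81.2% |

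The widening is relative to the SE that the model with age reports. The formula runs slightly above the simulation because it ignores the small cost of fitting age.

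With 80/40 or 110/30 subjects the power loss is 1.6-2.6 points at a difference of 0.2, and 4.2-5.9 points at 0.3.

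**3. Other shares.** For p from 0.15 to 0.45 the formula gives an SE wider by 0.4-0.8% at d = 0.25, 1.6-3.1% at d = 0.5 and 6-12% at d = 1.

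**4. Type I error.** Without age it is 4.5% at a difference of 0.3, which is on the conservative side. With age it stays at about 5% throughout.

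**5. Cost of keeping age when it explains nothing.** The SE is multiplied by about √(1 + 1/(N−5)). For N = 140 this is √(1 + 1/135) = 1.004. For N from 150 down to 60 the cost is 0.3% to 0.9%.

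**The case against.** The strongest reply is that age is already in the outcome. Baseline and Week 24 scores are each standardized at the subject's age in months at that visit, so their difference is net of the age trend in the reference charts, at a finer resolution than a two-level covariate. The SAP drops age only for this age-standardized outcome and keeps it for BMI and body weight, which suggests a deliberate choice. This stands in part. It makes a small stratum difference plausible, but it does not show that subjects with CF aged 12-17 and 18-20 change equally, and it does not explain why sex stays.

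The simulation is also simpler than the planned MMRM, and all its quantities are assumed. That stands: it shows a pattern and does not predict the loss in this trial.

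A reader might infer that the SAP contradicts the protocol. The documents do not support this. The protocol says only that the model is similar and leaves details to the SAP, whereas for ppFEV1 through Week 24 it requires exactly the same model. The SAP is also to be finalized before interim data lock and unblinding, so nothing points to a data-driven choice.

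**Conclusion.** The point holds as a minor one. The BMI z-score model omits a randomization factor that varies within the analysed subset, and the readable text gives no reason.

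The possible consequence is some loss of precision and an uncorrected chance imbalance among 18-20-year-olds. Under the assumed inputs the loss is negligible up to a difference of about 0.1. It becomes noticeable only at about 0.2, roughly 0.6 SD, which would be large for an age-standardized change.

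A reader might go further and conclude that the comparison definitely gives up precision, is biased, or has an invalid P value. None of these follows. The loss depends on a between-stratum difference that the documents do not give. Chance imbalance adds variance without a systematic direction. Type I error is at or below nominal.

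The consequence is limited further by the endpoint's status. BMI z-score is an other secondary endpoint, outside the testing hierarchy and without a power statement. BMI itself, a key secondary endpoint, keeps age in its model.

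**What to change.** In SAP 9.3.3.2, under change in BMI z-score, delete the clause that excludes age at screening and leave the restriction to subjects aged 20 or younger as it is. The model then adjusts for the randomization factor as the other MMRM analyses do.

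The cost is one phrase and one degree of freedom, with no new data. If age proves uninformative, the SE rises by less than 1%.

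If the sponsor prefers to keep the exclusion, one sentence should say why age but not sex is dropped, and a sensitivity analysis with age included should be prespecified.

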#### **9.4 Safety Analysis**

All safety analyses will be based on data from the TE period for all subjects in the Safety Set. Subjects will be analyzed according to the treatment they actually received in the Treatment Period. For subjects receiving study drug from more than one treatment group, the treatment group allocation will be the higher treatment group (VX-659/TEZ/IVA > TC Placebo).

The overall safety profile of the study drug will be assessed in terms of the following safety and tolerability endpoints:

- Treatment-emergent adverse events (TEAEs)
- Clinical laboratory values
- ECGs

- Vital signs
- Pulse oximetry

Only descriptive analysis of safety will be performed and no statistical testing will be performed.

#### **9.4.1 Adverse Events**

For analysis purposes, AEs will be classified as pretreatment AEs, TEAEs, or post-treatment AEs, defined as follows:

**Pretreatment AE:** any AE that occurred before the first dose date of study drug

**TEAE:** any AE that worsened (either in severity or seriousness) or that was newly developed on or after the first dose date of study drug through the end of the TE period

**Post-treatment AE:** any AE that worsened (either in severity or seriousness) or that was newly developed after the TE period

For AEs with completely missing or partially missing start dates, if there is no clear evidence that the AEs started before or after study treatment, the AEs will be classified as TEAEs.

Details for imputing missing or partial start dates of adverse events are described in [Appendix E](#).

An overview of all TEAEs by treatment group and overall will be summarized in the following categories:

- Number of TEAEs (total number of TEAEs only)
- Subjects with any TEAEs
- Subjects with TEAEs by strongest relationship
- Subjects with TEAEs by maximum severity
- Subjects with TEAEs leading to study drug discontinuation (discontinuation of any study drug)
- Subjects with TEAEs leading to study drug interruption (interruption of any study drug)
- Subjects with Grade 3/4 TEAEs
- Subjects with related TEAEs
- Subjects with serious TEAEs
- Subjects with related serious TEAEs
- Subjects with TEAE leading to death

The following summary tables of TEAEs will be presented by treatment group:

- All TEAEs
- Grade 3/4 TEAEs
- TEAEs by strongest relationship
- TEAEs by maximum severity
- TEAEs leading to treatment discontinuation

- TEAEs leading to treatment interruption
- Related TEAEs
- Serious TEAEs
- Related serious TEAEs
- TEAEs leading to death

Summaries will be presented by MedDRA SOC and PT using frequency counts and percentages (i.e., number and percentage of subjects with an event). When summarizing the number and percentages of subjects, subjects with multiple occurrences of the same adverse event or a continuing adverse event will be counted once, and only the maximum severity level will be presented in the severity summaries, and the strongest relationship level in the relationship summaries.

Additional summary tables will be presented by treatment for TEAEs showing number and percentage of subjects

- All TEAEs by PT

All AEs, including pretreatment AEs, TEAEs, and post-treatment AEs, will be presented in an individual subject data listing based on the All Subjects Set. In addition, a listing containing individual subject adverse event data for TEAEs leading to treatment discontinuation, TEAEs leading to treatment interruption, Grade 3/4 TEAEs, SAEs and all deaths will be provided separately, with a flag indicating the TEAE status for SAEs and deaths.

For all AEs, the eCRF captures the action taken for VX-659/TEZ/IVA pills separately from the action taken for IVA monotherapy pills. As a result, it is possible that, in the final database (after database lock), the AE actions taken for the two agents (fixed dose VX-659/TEZ/IVA and ivacaftor monotherapy) are different. The summaries and listings of “AE Leading to Treatment Discontinuation” and “AE Leading to Treatment Interruption” account for discontinuation and interruptions for either agent.

#### **9.4.2 Clinical Laboratory**

For the treatment-emergent laboratory assessments, the observed values and change from baseline values of the continuous hematology, coagulation and chemistry results will be summarized in SI units at each visit by treatment group.

The number and percentage of subjects meeting at least 1 threshold analysis criterion event during the TE period will be summarized by treatment group and overall. The threshold analysis

criterion shift from baseline will also be summarized for selected laboratory parameters. The threshold analysis criteria are provided in [Appendix F](#).

For select LFT laboratory tests (alanine transaminase [ALT], aspartate transaminase [AST], alkaline phosphatase [ALP], and total bilirubin), a scatter plot of the maximum treatment-emergent value versus the baseline value corresponding to  $\times$ ULN (upper limit of normal) will be presented. Further, a scatter plot of the maximum treatment-emergent value of ALT and AST, separately, versus the maximum treatment-emergent value of total bilirubin corresponding to  $\times$ ULN will also be presented by treatment group.

Results of positive urine/serum pregnancy test will be listed in individual subject data listings only. For positive serum pregnancy listing, subjects with serum HCG which are abnormally high will be selected.

In addition, a listing containing individual subject hematology, chemistry, and coagulation values will be provided. This listing will include data from both scheduled and unscheduled visits.

#### **9.4.3 Electrocardiogram**

For the treatment-emergent ECG measurements, a summary of observed values and change from baseline values will be provided at each visit by treatment group for the following ECG measurements (in msec): RR interval, PR interval, QT interval, and QTcF interval, QRS duration, and Heart Rate (beats per minute).

The number and percentage of subjects meeting at least 1 threshold analysis criterion during the TE period will be summarized by treatment group and overall. The threshold analysis criteria are provided in [Appendix F](#).

#### **9.4.4 Vital Signs**

For the treatment-emergent vital signs measurements, the observed values and change from baseline values will be summarized at each visit by treatment group. The following vital signs parameters will be summarized: systolic and diastolic blood pressure (mm Hg), body temperature ( $^{\circ}$ C), pulse rate (beats per minute), and respiratory rate (breaths per minute).

The number and percentage of subjects meeting at least 1 threshold analysis criterion during the TE period will be summarized by treatment group and overall. The threshold analysis criteria are provided in [Appendix F](#).

#### **9.4.5 Pulse Oximetry**

For the treatment-emergent pulse oximetry measurements, a summary of observed values and change from baseline values will be provided at each visit by treatment group, for the percent of oxygen saturation.

The number and percentage of subjects with shift changes from baseline (normal/missing and low according to the reference range) to the lowest percent of oxygen saturation during the TE period will be summarized by treatment group and overall.

#### **9.4.6 Physical Examination**

Abnormal PE findings will be presented as an individual subject data listing only.

## 10 SUMMARY OF INTERIM AND DMC ANALYSIS

For each DMC meeting and the planned IA, the Vertex Biometrics Department will prepare the analysis package using the dummy treatment code and dummy spirometry and SwCl data according to the DMC charter and the DMC SAP, respectively; SAS (Version 9.4, or higher) will be used to generate all statistical outputs (tables, figures, listings, and datasets).

ICON Clinical Research Limited (ICON), appointed as the independent biostatistician, will perform the IA according to the DMC SAP using the SAS code provided by Vertex Biometrics Department, the unblinded treatment code, the real (restricted) spirometry, and the real (restricted) sweat chloride data. Unblinded treatment code, spirometry, and sweat chloride data will be transferred directly from relevant vendors to the independent biostatistician. ICON will present the results to the DMC.

If the study crosses the efficacy boundary according to the pre-specified criterion (Section 7.5), a limited Vertex unblinded team may be unblinded to the study. The limited Vertex unblinded team will use the unblinded treatment code and real (restricted) data to generate statistical outputs and prepare for submission(s). Members of the limited Vertex unblinded team will not be involved in or influence the conduct of the remaining part of the study to protect the integrity of the study.

